12.2.3. On treatment evaluations

Participants in all arms will have brief on-treatment evaluations at 4, 8 and 12 (end of treatment) weeks after the entry visit (treatment start).

A minority of participants will receive 24 weeks of treatment and so will have additional ontreatment evaluations at 16, 20 and 24 (end of treatment) weeks.

Because some of these visits include medication pickup, the goal is to conduct the visits within a +/- 2 day window. However, up to a +5 / -14 day window will be permissible for visits with medication pick up (visits outside this window are allowed if approved by study doctor).

The following assessments will be done

- Scan biometric to confirm identity
- Administer a brief survey on substance use, risk behavior and medication adherence, record answers in eCRF
- Update medication history
- Provide updated contact/locator information
- Count the pills remaining in the prior bottle
- Provide the next bottle of medication (Arms 1 and 2 only; at all except 12 week visit)
- Observe that day's dose if it has not been taken
- Draw blood for repository (Week 12 [or Week 24] visit only)
- Pregnancy test (if female and pregnancy suspected)
- Assess adverse events
- Schedule next appointment

While COVID-19 safety precautions are in place, we will attempt to complete these visits with minimal face-to-face contact and so will offer alternatives. For the on-treatment evaluations, we will complete surveys, updating of locator information and counseling over the phone. We will offer multiple options for medication refills other than pickup at the ICC including drop off to home or some other mutually agreed upon location. Prior bottles will be collected and stored for several days before pills are counted. For the end of treatment visit, surveys will be completed over the phone but an in-person visit will be preferred for the blood draw. Exceptions will be made for this in-person requirement in cases where 1) COVID-19 precautions make travel to the site challenging; and 2) participants are in rehabilitation facilities (e.g., drug detoxification programs) or cannot travel to the site for another reason.

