11.1.1. Arm 1. Low intensity HCV treatment adherence support

11.1.1.1. Arm 1. Medication delivery. The standard of care in India is 4-weekly dispensation of medication at three appointments over a 12-week period. Participants assigned to this Arm will have their medications dispensed as per this standard of care. At the Study Entry Visit, participants will receive their first bottle of medication. During treatment, participants in this Arm will receive their study medications 1) at their home (delivered by a PN); 2) a chosen location (delivered by a PN); or 3) at the ICC. Medication drop-off/pick up will be required two additional times after treatment initiation (five times for those receiving 24 weeks of treatment) for refills. Medication drop-off/pick up will be scheduled a few days before the 28-day supply of medication is set to run out. The decision as to the mode for medication drop-off/pickup will be based on precautions in place for COVID-19 which are designed to maximize participant/staff safety.

11.1.1.2. Arm 1. Adherence Support. Participants in this arm will receive standard adherence support. The standard adherence support in India entails general adherence counseling and tracking for missed medication refill pick-ups.

At the Entry Visit, the study nurse and a counselor will provide standard counseling on HCV treatment, the importance of treatment adherence and risks of reinfection. The counseling protocol which includes pictorial guides is based on a combination of what is used in India and has been developed for PWID in the US (See **Study MOP** for details). This standard counseling will be repeated at each of the additional medication pick-up/drop-off visits. Counseling will happen either 1) over the phone; or 2) in person depending on precautions in place for COVID-19.

Participants in this arm will be provided with a phone number to call with any problems related to study treatment and/or side effects as needed.

11.1.1.3. Arm 1. Linkage to other services. The **Resources List** that will be maintained at each ICC will provide a list of resources at the ICC (e.g., OAT) and within each city (e.g., government social protection schemes). Participants in this arm will have access to all ICC services including testing and care for HIV, STI management, TB testing and linkage, counseling, condoms, OAT, SSP and will be provided with other service referrals as needed.

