Counseling: Counselors in the ICCs have been trained in motivational interviewing. They provide individual, couples and group level counseling at the ICCs. Focused areas include treatment adherence, substance use including alcohol use, depression and other mental health comorbidity as well as disclosure issues around sexual identity and HIV status. Individuals who need additional support for alcoholism or mental health issues are referred.

Other specific services which are not available onsite and will require referral include inpatient treatment for drug and/or alcohol use, pharmacologic treatment for alcohol use, TB treatment and mental health services.

11.1.1.4. Arm 1. Participant tracking. Tracking efforts will be triggered by missed medication refill pickups. PN will generate daily reports of participant attendance to determine who has missed a refill appointment. As soon as a participant misses a refill pickup, tracking will be initiated. At least three attempts will be made to contact each participant using different approaches at different times of the day. The first attempt will be via the participants mobile phone (if the participant has a phone). Additional attempts should include a visit to the participant's home and/or hangout locations as specified in the locator form and as needed unless there is evidence of death or migration.

PN will continue to attempt to contact participants up to 2 weeks after the medication refill appointment is missed. After 2 weeks, tracking attempts for medication refill appointments can be ceased. However, participants will still be tracked for SVR evaluation visit.

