11.1.2. Arm 2. Medium intensity HCV treatment adherence support

11.1.2.1. Arm 2. Medication delivery. The standard of care in India is 4-weekly dispensation of medication at three appointments over a 12-week period. Participants assigned to this Arm will have their medications dispensed as per this standard of care. At the Study Entry Visit, participants will receive their first bottle of medication. During treatment, participants in this Arm will receive their study medications 1) at their home (delivered by a PN); 2) at a chosen location (delivered by a PN); or 3) at the ICC. Medication drop-off/pick-up will be required two additional times after treatment initiation (five times for those receiving 24 weeks of treatment for refills. Medication drop-off/pick up will be scheduled a few days before the 28 day supply of medication is set to run out. The decision as to the mode for medication drop-off/pick up will be based on precautions in place for COVID-19 which are designed to maximize participant/staff safety.

11.1.2.2. Arm 2. Adherence support. Participants in this arm will receive tailored PN adherence support that seeks to address individual barriers and leverage facilitators to adherence to treatment and medication refill appointments.

A PN is a staff member who is knowledgeable about local HIV care, substance use, harm reduction and mental health services (e.g., government social protection schemes) such that they can facilitate linkage to other services that are needed and can promote adherence to hepatitis C treatment. PN will also dually serve as counselors as needed.

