11.2.1. Regimens

For participants without HIV infection and who are HIV-infected but not on an efavirenz containing regimen, the treatment will be once-daily generic oral fixed-dose combination of sofosbuvir/ velpatasvir (SOF/VEL) containing 400 mg of SOF and 100mg of VEL. Treatment duration will be 12 weeks taken orally with or without food. If a participant is co-infected with HIV and on an efavirenz containing regimen they will have the option to switch to a non-EFV containing regimen (e.g., DTG) for at least two weeks prior to initiation of DAA therapy with SOF/VEL. The government of India is modifying their guidelines and a combination of tenofovir/emtricitabine/dolutegravir TDF/FTC/DTG will be the preferred first-line regimen. The government is expected to roll-out this combination in December 2019 ahead of the initiation of this trial.

If the participant is unable to modify the ART regimen to a non-EFV containing regimen, they will receive once-daily generic oral fixed-dose combination of sofosbuvir/daclatasvir (SOF/DAC) including 400 mg of SOF and 60 mg of DAC (an additional 30 mg pill of DAC will be dispensed as

required). Treatment duration for this group will be guided by the presence/absence of compensated cirrhosis and genotype. For those with genotype 3 infection and compensated cirrhosis, treatment duration will be 24 weeks. For all others, treatment duration will be 12 weeks. All treatment will be oral with or without food.

For Arms 1 and 2, the Study Nurse will observe the first dose being taken by the participant upon completion of all entry evaluations. Participants will receive only one bottle of study product at a time.

Participants in Arms 1 and 2 will be scheduled to have a scheduled pick-up/drop off for the next bottle of study medication three days prior to when their last pill is due from that bottle. Participants will be asked to retain empty study bottles and return them to the study staff.

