When a study participant initiates HCV treatment through the trial at one of the community-based centers, contact will be made with the study pharmacy. The study medications will be packaged by a study team member under the supervision of the local pharmacist into the required containers (bottles/packs for Arms 1 and 2 and pillboxes for Arm 3). The medication label will comply with local Indian guidelines. A peer navigator/logistics assistant will transport a one month supply of medication for participants in Arms 1 and 2 from the study pharmacy to the ICC/location for drop-off where each participant will receive the medication from the study nurse or a peer navigator. When the participant is due for a refill, the logistics assistant will pick up the next supply of medication on the morning when the participant is due for that refill. If the participant cannot be reached for pick-up/drop-off of a refill, the medication will be returned to the pharmacy and picked up again the following morning such that it will be stored for a maximum of 12 hours on site at the ICC. For arm 3, a one-week supply of medication (in a pillbox) will be picked up from the pharmacy and handed over to the participant as per the frequency of DOT assigned.

11.2.2.2. Study product accountability. The Site Pharmacist will be required to maintain complete records of all study products received from the Central Pharmacy and subsequently dispensed. First the medication will be labeled and handed off to the site personnel for transport to the ICC/participant. Chain of custody will be documented from the point of shipping from the Central Pharmacy to study staff to the final point when medications are handed over to a study participant. At this point, biometric identification will be used to document receipt of the medication by the participant.

All unused study products must be returned to the Central Pharmacy after the study is completed or terminated. The Central Study Pharmacist will follow appropriate protocols for destruction of unused study products.

Medications provided by local government/hepatitis C treatment programs will be logged and tracked in a separate system. The Site Pharmacist will follow appropriate protocols for destruction of unused product.

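### Section 12.2.3 exempts only the week-12 visit from the Arm 1 and 2 refill, which mis-times one bottle for the few participants on 24-week courses (low severity)

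*Protocol*

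**What the plan says.** Protocol Section 12.2.3 sets on-treatment visits at weeks 4, 8 and 12 for everyone, and at weeks 16, 20 and 24 as well for participants on 24-week courses. It marks week 12 as the end of treatment for the former and week 24 for the latter. A single task list then serves all these visits. Its dispensing item is "Provide the next bottle of medication (Arms 1 and 2 only; at all except 12 week visit". In the same list, the repository blood draw is tied to week 12 with week 24 as a bracketed alternative. The dispensing item has no such bracket.

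Section 11 gives the supply rules:

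- **Who has 24 weeks.** Section 11.2.1, for co-infected participants on sofosbuvir/daclatasvir because they cannot leave efavirenz: "For those with genotype 3 infection and compensated cirrhosis, treatment duration will be 24 weeks".
- **How many refills.** Section 11.1.1.1 (Arm 1): "Medication drop-off/pick up will be required two additional times after treatment initiation (five times for those receiving 24 weeks of treatment) for refills". Section 11.1.2.1 gives the same counts for Arm 2.
- **When.** Section 11.1.2.1: "Medication drop-off/pick up will be scheduled a few days before the 28 day supply of medication is set to run out". Section 11.2.1 is more exact, scheduling Arms 1 and 2 for a "pick-up/drop off for the next bottle of study medication three days prior to when their last pill is due from that bottle".
- **No reserve.** Section 11.2.1: "Participants will receive only one bottle of study product at a time".

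**The concern.** The exemption in 12.2.3 is tied to a week number, when what makes a refill unnecessary is the end of the course. For a 12-week course the two coincide. For a 24-week course they do not: week 12 is the midpoint, where a bottle is needed, and week 24 is the end, where it is not. The total number of bottles is unchanged, so a count of bottles dispensed would not show the problem.

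At stake is an interruption of antiviral treatment halfway through the course, with no spare supply, in participants with genotype 3 infection and compensated cirrhosis. Section 12.2.3 is also the only visit-by-visit dispensing list that covers 24-week courses. The Section 9 arm descriptions stop at the week-8 bottle. Table 12.1 has no dispensing row, and its on-treatment columns end at week 12.

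**Working it through.** **Inputs.** 28 pills per bottle, one dose a day, first dose observed at entry (day 0); refill counts and the three-day rule from Sections 11.1.1.1, 11.1.2.1 and 11.2.1; visit weeks and windows from Section 12.2.3 (goal ±2 days; up to +5/−14 days for pick-up visits). Full adherence is assumed, so there are no leftover pills.

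**1. Reproduce the stated refill counts.** Refills = (weeks × 7 / 28) − 1.

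- 12 weeks: 84/28 − 1 = 2.
- 24 weeks: 168/28 − 1 = 5.

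Both match Section 11.

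**2. Refill days under Section 11.** The last pill of bottle *k* is taken on day 28*k* − 1, so the refill falls three days earlier, on day 28*k* − 4. For *k* = 1 to 5 this gives days 24, 52, 80, 108 and 136. Each is 4 days before a nominal visit day (28, 56, 84, 112, 140), that is, weeks 4, 8, 12, 16 and 20. The last refill, day 136, is 32 days before the nominal week-24 visit (day 168). In the permissible pick-up windows (7*w* − 14 to 7*w* + 5), day 80 falls only in that of week 12 (days 70 to 89), and no refill day falls in that of week 24 (days 154 to 173).

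**3. Compare the two readings for a 24-week course.**

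| | Refill weeks | Refills | Days without drug | Left over at week 24 |
|---|---|---|---|---|
| Section 11 | 4, 8, 12, 16, 20 | 5 | 0 of 168 | 0 doses |
| 12.2.3 list, literal | 4, 8, 16, 20, 24 | 5 | 28 (days 84 to 111) | 28 doses |

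For a 12-week course the literal list gives refills at weeks 4 and 8, 84 doses and no gap, in agreement with Section 11.

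**4. Length of the gap if the list alone is followed.** Supply from the first three bottles ends at max(84, week-8 visit day + 28). The unbroken gap runs from there to the week-16 visit.

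- Nominal: 112 − 84 = 28 days.
- Goal windows: week-8 visit no later than day 58, so supply ends on day 84 to 86; week-16 visit on day 110 to 114. Shortest 110 − 86 = 24, longest 114 − 84 = 30 days.
- Permissible windows: week-8 visit no later than day 61, so supply ends on day 84 to 89; week-16 visit on day 98 to 117. Shortest 98 − 89 = 9, longest 117 − 84 = 33 days.

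In the 9-day case the late week-8 visit has already cost 5 days (61 − 56). Total undosed days before the week-16 bottle equal the visit day minus the 84 doses supplied: 98 − 84 = 14 to 117 − 84 = 33, or 26 to 30 within the goal windows. A late week-4 visit does not alter these ranges. Leftover pills would shorten the gap, and visits outside the windows, which the study doctor may approve, could fall outside these figures.

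**5. Number affected.** Not given beyond the description of this group as a minority. The conditions are HIV co-infection, no switch from efavirenz, genotype 3, compensated cirrhosis, and allocation to Arm 1 or 2.

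**The case against.** The strongest reply is that this is a copy-editing slip that nobody would act on. Section 12.2.3 itself identifies week 24 as the end of treatment for the longer course, and the protocol is largely written to a 12-week template, so the week-12 label is natural shorthand. Section 11 states the dispensing rules outright, and a task list that omits a bottle at week 12 does not forbid the refill that Section 11 schedules separately, possibly as a home or field delivery.

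There are also safeguards. Supply is tied to the refill date ("When the participant is due for a refill, the logistics assistant will pick up the next supply of medication on the morning"). In Arm 1, "PN will generate daily reports of participant attendance to determine who has missed a refill appointment", with the same tracking in Arm 2. Arm 2 participants have navigator contact at least every two weeks and a reminder two days before each refill. Physicians write all prescriptions, specialist guidance is available for compensated cirrhosis, and interruptions of more than 7 days must be reported.

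Most of this stands, and it is why the severity is low. It does not make the item correct. Tracking starts from a missed refill appointment, and someone who attends week 12 and is given no bottle, as the list directs, may not be counted as having missed one. Reporting an interruption comes after it has happened.

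A narrower objection is that the +5/−14-day window applies only to pick-up visits, so on the literal reading it would not apply to week 12. That is fair as far as the window comparison goes. The conflict does not depend on it: the three-day rule puts a refill 4 days before week 12 and none near week 24.

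**Conclusion.** The point holds at low severity. For 24-week courses in Arms 1 and 2, the literal dispensing item in 12.2.3 contradicts Section 11 on the timing of one refill: the week-12 bottle is moved to week 24. The refill count agrees. If a site relied on the 12.2.3 list alone, the unbroken gap would be 28 days nominally, 24 to 30 days within the goal windows and 9 to 33 days within the permissible windows, assuming full adherence. If it follows Section 11, there is no gap.

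This reads as a wording slip and not a deliberate pause, since nothing in the protocol gives a reason to stop at week 12 and the blood-draw item in the same list was adapted for the longer course. That the group is very small is an inference from the conditions for 24-week treatment and from the switch to dolutegravir that Section 11.2.1 offers and expects to become usual. Sample size, power, the endpoint definition and the primary analysis are unaffected. The Manual of Operations and the eCRF, which may already handle this correctly, are not among the documents.

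**What to change.** Reword the dispensing item in Section 12.2.3 to: *Arms 1 and 2 only; at all visits except the end-of-treatment visit (Week 12 [or Week 24])*. Refills then fall at weeks 4, 8, 12, 16 and 20, giving 168 doses with no gap and no surplus bottle. Check that the matching eCRF prompts for a bottle at week 12, and not at week 24, on the longer course. If 24-week courses have already been completed, check their dispensing records for the weeks 12 to 16 interval.

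Optional tidying in the same amendment: Section 12.3.10 places the extra adherence assessments at weeks 18 and 24, whereas Sections 11.2.3 and 12.2.3 imply weeks 16, 20 and 24. This is a separate matter from dispensing.

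The cost is one reworded item, one form check and, optionally, one further phrase. No visits or drug are added.

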12.2.4. SVR evaluations

SVR evaluations will be assessed on the majority of participants at week 24 (12 weeks after treatment completion). For a minority of participants who receive 24 weeks of treatment, the SVR evaluations will take place at week 36. The window for the SVR assessment visit will be -2 weeks (10 weeks after treatment completion) to 60 weeks after treatment completion (i.e., study weeks 22-72). Visits outside this window are allowed with documentation of reason for early/late visit.

If a participant misses the visit window, every attempt should be made to contact participant and complete the SVR evaluation and other evaluations through the end of the study follow-up period.

At this visit, the following assessments will be done in all arms

- Scan biometric to confirm identity
- Administer a brief survey on substance use, risk behavior and quality of life
- Update medication history
- Provide updated contact/locator information
- EHR review, clinical exam, and vital signs
- Draw blood for HCV RNA testing
- Abstract HIV RNA information from government ART book (if HIV infected)
- Pregnancy test (if female)
- Schedule next appointment

The post-SVR evaluations will be scheduled in relation to when participants complete the SVR evaluations.

While COVID-19 safety precautions are in place, in order to reduce face-to-face contact, we will administer surveys, update medication history and collect locator information over the phone. Participants will have to come to the ICC for a brief exam and blood draw (and pregnancy test as needed). Exceptions will be made for this in-person requirement in cases where 1) COVID-19 precautions make travel to the site challenging; and 2) participants are in rehabilitation facilities or cannot travel to the site for another reason.

In cases where the HCV RNA ≥30 IU/ml and <1000 IU/ml, a repeat sample will be drawn ≥14 days after the initial sample as long as it is within the SVR window (i.e., up to 60 weeks after treatment completion)

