In this trial, treatment completion was achieved by 88% in each arm. While ongoing drug injection was only reported by a minority in this sample, greater than 50% reported active use of some substance. For persons on the 12-week regimen, the median number of doses missed per person was 4. In addition, 40% of participants requested take-home doses at some point during the 12 weeks (median: 2.5 doses per person requesting). The primary reason for requesting take home doses was travel. Importantly in the arm that received 12-weeks of therapy, there was no difference in treatment completion or SVR by ongoing drug use.

These data speak to the feasibility of field-based DOT and its success in persons with ongoing substance use. In this study, one field worker was able to manage about 30 clients at a time. However, there were some logistical challenges, and it was clear that some clients could have maintained high adherence without daily contact. This provides the rationale for our current protocol where this strategy will not be used for all participants randomized to the high intensity support strategy but will be assigned to clients with very specific support needs/barriers.

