^{*}For participants who receive 24 weeks of therapy, the SVR visit will take place at 36 weeks

^{**}For participants who receive 24 weeks of therapy, these visits will take place at weeks 60, 84, 108, 132, 156, 180, 204, 228

^{***}Additional doses will be observed for Arm 3 (36 to 84 for those receiving 12 weeks of treatment and 72 to 168 for those receiving 24 weeks)

^{****}Only assessed on participants who achieve HCV cure

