12.2.8. Premature treatment discontinuation evaluations

Participants who plan to discontinue treatment or who have discontinued their study medication prior to completing the full 12-week (or 24-week) course will have been instructed to contact the site to alert them of premature discontinuation. These participants will be encouraged, like all other participants, to return for their SVR evaluation visit at week 24 and remain on the study through study completion. No adjustments to the timing of the SVR evaluation will be made for premature treatment discontinuation. Participants will be provided a number to call or send a text message informing the site of the stop date.

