Effect of delays in treatment completion on SVR. Additional exploratory analyses will evaluate the impact of non-adherence and delays in completing treatment on SVR. Initial analyses will incorporate data from all three arms. Two variables will be calculated: 1) the percentage of doses completed (as described above); and 2) days to treatment completion. While the scheduled course of treatment will be 84 days for most, participants will be instructed to take all of the doses prescribed (even if doses are missed and the total time for treatment completion extends beyond 84 days. In separate models, log-binomial regression will be used to estimate the association between 1) estimated adherence; and 2) days to treatment completion and SVR. These analyses will be combined across risk strata and treatment arm but these variables will be included as covariates. Additional analysis will be conducted exclusively among participants assigned to Arm 3 (high intensity support) where adherence data will be objectively collected using biometric data.

Estimation of heterogeneity in treatment effect and estimation of average treatment effect.

Additional analyses will be completed to estimate heterogeneity in treatment effect and the average treatment effect for the primary (SVR) and secondary outcomes (treatment completion) defined above.

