18.2.2. Prisoners

It is possible that persons who are enrolled become prisoners during the course of the study. This means that they may become prisoners while they are taking HCV treatment. We do not have formal agreements in place to provide study treatment while participants are in prison. However, we will work with the prisons in each of the cities to establish agreements where possible. The goal will be to support study participants to complete their course of treatment while in prison by either delivering treatment through peers, family members and or other prison staff. However, we will not conduct any research activities while study participants are in prison. This means that intervention support activities will cease and no formal data collection will be conducted and study

visits will be classified as "missed" while participants are in prison. We will continue to track them so that when they are released we can reengage them in clinical care and study activities as appropriate.

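### The study-week figures given for the SVR window fit only treatment completed at week 12, and the week-24 visit named for early stoppers conflicts with week 36 for 24-week courses (minor)

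*Protocol*

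**What the plan says.** The primary endpoint (Protocol 15.2.1 and 15.7.2.1, SAP section 1) is HCV RNA below the quantification limit between 10 and 60 weeks after treatment is completed. Three places turn this into visit timing.

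- **Protocol 12.2.4** places the visit at week 24 for most participants and at week 36 for those on a 24-week course. It then gives one window for everyone, from 10 weeks to "60 weeks after treatment completion (i.e., study weeks 22-72). Visits outside this window are allowed with documentation of reason for early/late visit".
- **Protocol 12.1**, in the footnote to the schedule, agrees on the visit week: "For participants who receive 24 weeks of therapy, the SVR visit will take place at 36 weeks".
- **Protocol 12.2.8** covers early stopping of both the 12-week and the 24-week course. It asks these participants to "return for their SVR evaluation visit at week 24 and remain on the study through study completion", and adds that early stopping does not change when the SVR evaluation takes place. It gives no alternative week for the longer course.

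**The concern.** A window counted from completion cannot be the same run of study weeks for a 12-week and a 24-week course. A site that works from the study-week figures could accept a sample from a 24-week participant who is still on treatment, or turn away one drawn late but within the defined window. Section 12.2.8 contradicts itself for the 24-week course: unchanged timing would mean week 36, yet it names week 24. Followed as printed, it can produce a sample that is too early for the endpoint. This is the primary endpoint of an unblinded trial, so its operating instructions should agree with its definition.

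**Working it through.** **Inputs.** The window opens 10 weeks and closes 60 weeks after completion (Protocol 12.2.4, 15.2.1). The stated study weeks are 22 to 72 (12.2.4). The planned visit is week 24 for a 12-week course and week 36 for a 24-week course (12.1, 12.2.4). The visit named for early stoppers is week 24 (12.2.8).

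**1. Window in study weeks.** For completion at study week T, the window is T + 10 to T + 60.

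- T = 12: 12 + 10 = 22 and 12 + 60 = 72. This reproduces the plan's figure.
- T = 24: 24 + 10 = 34 and 24 + 60 = 84.

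For a 24-week course finished on time, the printed and the correct windows share weeks 34 to 72, which is 72 − 34 = 38 of 50 weeks. The printed window wrongly includes weeks 22 to 34 (12 weeks, of which 22 to 24 fall before the course ends). It wrongly excludes weeks 72 to 84 (12 weeks, or 48 to 60 weeks after completion). These are calendar weeks, not participants. The planned week-36 visit lies inside both windows, so only visits away from schedule are affected.

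**2. Early stoppers of a 24-week course.** For a last dose at week S and a sample at week V, the interval is V − S. At V = 24 it is below 10 weeks whenever S > 14.

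| Last dose (week) | Weeks to a week-24 sample | Weeks to a week-36 sample |
|---|---|---|
| 12 | 12 | 24 |
| 14 | 10 | 22 |
| 16 | 8 | 20 |
| 20 | 4 | 16 |
| 23 | 1 | 13 |

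If completion is instead read as the planned end of the course, the window is weeks 34 to 84 whatever the stop date. Week 24 is then 34 − 24 = 10 weeks before it opens, and week 36 is inside it. So week 24 meets the 10-week limit only if the last dose is the anchor and falls by week 14. Week 36 meets it on either anchor.

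**3. Early stoppers of a 12-week course.** Week 24 is 23 weeks after a stop at week 1 and 13 weeks after a stop at week 11, inside 10 to 60 in each case. The conflict is confined to the 24-week course.

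**4. Who is on a 24-week course.** Under Protocol 11.2.1 a participant must be HIV co-infected, on an efavirenz regimen that cannot be changed, and have both genotype 3 infection and compensated cirrhosis. Section 12.3.9 limits genotype testing to co-infected clients with cirrhosis on efavirenz-based ART. The documents give no count.

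**The case against.** The strongest reply is that nothing in the analysis depends on the study-week figures. Every statement of the endpoint counts from completion, and 12.2.4 itself closes by describing the window as running to 60 weeks after completion. Week 24 in 12.2.8 may be shorthand for the majority: 14.2 also writes only week 24 for unplanned pregnancy visits, where 12.2.7 gives week 24 or week 36. The sentence on unchanged timing points to week 36. This largely stands, and it is why the point is minor. It does not make the printed weeks right for a 24-week course, nor remove the contradiction in 12.2.8.

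A reader might infer three stronger things.

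- **That late finishers of a 12-week course are commonly sampled too early.** The plan does expect some courses to run long: "participants will be instructed to take all of the doses prescribed (even if doses are missed and the total time for treatment completion" may extend beyond 84 days. But 12.2.3 says that "up to a +5 / -14 day window will be permissible for visits with medication pick up". A 5-day delay leaves a week-24 sample at 12 − 5/7 = 11.3 weeks, and two such delays added together leave it at 12 − 10/7 = 10.6 weeks, both in window. A problem at week 24 needs more than 14 days of delay. The window also already counts from completion.
- **That out-of-window results cannot be scored in the primary analysis.** Such results are foreseen: "If a participant misses the visit window, every attempt should be made to contact participant and complete the SVR evaluation". The primary missing-data rule names only loss to follow-up and death. But everyone randomized is analysed, success requires a result at 10 to 60 weeks, and the sensitivity text (Protocol 15.7.2.1, SAP 1b) treats no visit within the window as missing. Failure can therefore be inferred. What is lacking is an explicit sentence.
- **That the comparison between arms is biased.** The documents give no rates of out-of-window sampling by arm, so neither size nor direction can be derived.

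**Conclusion.** The point holds as two errors in operating instructions. The study weeks in 12.2.4 are right only for completion at week 12, and an on-time 24-week course should read 34 to 84. Section 12.2.8 conflicts with 12.1 and 12.2.4 for early stoppers of a 24-week course and, followed as printed after a stop later than week 14, gives a sample under 10 weeks from the last dose. The arithmetic rests only on the protocol's own 10-to-60-week rule. The interval for early stoppers is measured from the last dose because the plan does not say what completion means for them. The endpoint definition is unaffected and the exposed group is very small, though it cannot be counted from the documents. Severity: minor.

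**What to change.** 1. **Protocol 12.2.4:** replace the single study-week range with weeks 22 to 72 for a 12-week course and 34 to 84 for a 24-week course when completed on time, and otherwise count from actual completion.
2. **Protocol 12.2.8:** reconcile the visit week with 12.1 and 12.2.4 for early stoppers of a 24-week course. State one anchor for the window of anyone who stops early, consistent with that section's own rule that timing does not change. Moving the anchor to the last dose would not be neutral: a 12-week course stopped at week 2 would have a window of weeks 12 to 62 instead of 22 to 72.
3. **Optional, for consistency with the sensitivity text:** in the per-protocol definition (Protocol 15.7.2.1, SAP 1a), require that the SVR visit was completed within the window. In SAP section 1, state that a participant with no in-window result counts as not achieving SVR.

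Items 1 and 2 cost about a line each and change neither the endpoint nor the sample size. Item 3 adds two short phrases. Its cost is that a cured participant tested only outside the window is scored as a failure, which the endpoint definition already implies.
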